loss¹⁸⁻²¹. Animal models of primary hepatic IR demonstrate the causal role of hepatic dysfunction in the development of NAFLD, T2D and CVD^{22,23}. IR in muscle, liver and adipose tissue are reported in PCOS adults²⁴⁻²⁷, and we found the same in girls with PCOS, despite their young age. The synergy between obesity and hyperandrogenism relate to alterations in fat metabolism, inflammation, NAFLD and IR in PCOS adults²⁸⁻³⁰. Our proposed mechanism for development of excess liver fat from adipose and hepatic IR is shown in Figure 1. *An understanding of the complex physiology between tissue-specific IR, hepatic fat and androgens in PCOS is lacking. Addressing this gap is my intermediate goal and is an aim this protocol.*

c) Current research methods to assess IR

Research methods to assess early tissue-specific IR require complex protocols and few models exist which incorporate oral feedings³¹⁻³³. Current data for evaluating both hepatic and adipose IR have employed intravenous (IV) approaches, which fail to account for contributions of hormones such as glucagon, glucagon like peptide (GLP-1) or leptin, which may play a crucial role in hepatic and adipose signaling²⁰. Further, the maximum exogenous insulin doses that can be administered safely IV often produce lower serum insulin concentrations than generated endogenously following an oral glucose load, and the prolonged fasting required for IV studies is at the limit of tolerability in youth. *Thus, a gap exists in the methodology to assess hepatic glucose metabolism and adipose IR in a comprehensive, minimally-invasive, yet physiologic setting. Addressing this gap is the first step towards addressing my long terms goals and is a focus of this protocol.*

A. Preliminary Studies/Progress Report:

SA1: Optimize novel minimally-invasive physiologic methods to study liver metabolism

SA 1 Pilot Data on Liver fat and Insulin Resistance in youth with T2D: In our recent adolescent studies,

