we examined the differential tissue-specific expression of IR in youth with T2D and PCOS utilizing a sophisticated 3 stage hyperinsulinemic euglycemic clamp with multiple stable isotope tracers. By contrasting patterns of pathology between PCOS, obese controls and T2D we are uncovering subtle differences suggesting unique mechanisms of hepatic IR in PCOS. T2D youth appear similar to T2D adults in having adipose, hepatic and muscle IR. However, the IR is more severe than in adults, with unexpectedly progressed markers of CVD and NAFLD at diagnosis despite their young age³⁴. Adipose IR in our T2D youth is exhibited by a persistent glycerol rate of appearance (Ra) despite very high induced insulin concentrations (200 mU/L) and hepatic IR is demonstrated by a doubling in the insulin concentration required for 50% suppression of glucose Ra (IC50 Ra)(Figure 2A). This IR translates to persistent elevations in serum free fatty acids (FFA) and glucose in these individuals. Elevated hepatic fat content (Figure 2B) correlates with both elevated serum FFA concentrations and glycerol Ra in T2D, indicating that hepatic steatosis is related to adipocyte IR. Muscle IR, assessed by glucose clearance rate, is very tightly correlated with both glycerol Ra and serum FFA concentrations during hyperinsulinemia, indicating that adipocyte IR may impact muscle IR as well. Finally, our T2D youth have muscle mitochondrial dysfunction as assessed with ³¹P magnetic resonance spectroscopy (MRS), which relates to muscle IR.

Figure 2: Hepatic Measures in Girls

[figure not shown]

Table 1: Serum Markers in Obese Girls

	Control	PCOS	T2D
Number	19	38	40
AST (IU/L)	19±2	36±2	32±2
ALT (IU/L)	29±3	38±3	40±2
Triglycerides (mg/dL)	78±8	129±7	207±7
Adiponectin (ng/dL)	8.4±0.9	5.8±0.4	5.7±0.1
Leptin (ng/dL)	37±6	43±3	36±1
CRP (ng/dL)	1.7±1.4	4.3±0.6	4.1±0.1
HbA1C (%)	5.1±0.2	5.4±0.3	7.2±0.4
Oral Disposition Index (oDI)	5.2±2.2	3.2±0.5	N/A
Fasting FFA (mmol/l)	523±37	629±22	N/A
FFA n7 (nmol/g)	29±13	45±15	N/A

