MRI-assessed rates of hepatic steatosis even higher than in T2D girls (Figure 2B). Hepatic fat in PCOS girls is weakly associated to markers of overall lipolysis, but is more closely related to visceral adipose tissue (VAT) and plasma markers of hepatic *de novo* lipogenesis (FFA n7, Table 1). Further, during IV-induced hyperinsulinemia during the clamp, girls with PCOS have lower rates of carbohydrate oxidation than obese controls (0.013 ± 0.0001 vs. 0.017 ± 0.002 mmol/min/kg), indicating preferential storing of glucose as evidence of metabolic inflexibility. Finally, markers of CVD, including carotid plaque development and exercise tolerance are similar between PCOS and T2D, indicating that PCOS status may be a significant risk factor for CVD even in youth. In summary, in youth with PCOS, excess liver fat may relate to adipose IR, hepatic IR and metabolic inflexibility with increased *de novo* lipogenesis from carbohydrates. Targeting improved understanding of these pathologic processes in a physiologic model is a logical step for reducing progression of T2D, CVD and NAFLD in PCOS youth.

[figure not shown]
Preliminary data from oral glucose tolerance tests in girls with PCOS:

Obese girls with PCOS have high 2 hour oral glucose tolerance test (OGTT) glucose and insulin concentrations (Figure 3 A and B). Of note, the PCOS OGTT insulin concentrations are higher than those achieved during the clamp 245 ± 40 IU/ml). Despite the relative hyperinsulinemia, they have poor insulin secretion relative to IR, i.e. a lower OGTT-derived oral disposition index (oDI) vs. obese controls (Table 1) indicating the presence of both β -cell dysfunction and IR. Girls with PCOS and an oDI of <1 , an established risk for T2D³⁵, have half the insulin sensitivity vs. those with an oDI of >1 (5.3 ± 2.1 vs. 10.8 ± 0.8 mg/kg lean/min). Thus it may be that inadequate insulin secretion during an OGTT allows for persistent lipolysis and gluconeogenesis, which increases hepatic fat content and worsens muscle IR. GLP-1 and leptin, both hormones affected by oral ingestion, may be involved in this physiologic interplay, which is completely ignored with hyperinsulinemic clamp IV glucose delivery. The combination of isotope tracers and oral nutrient delivery is required to answer this critical question. This data is one of the primary reasons that we need to move to an oral model.

Pilot Data on Liver fat and Insulin

Resistance in youth with PCOS:

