The protocol as described includes the entire subject set, which allow for comparisons between obese girls with and without PCOS. OGTT with tracers will be conducted in all subjects, and overnight assessment of HDNL in 20 subjects (10 with PCOS and 10 without). However, data from the first 6-12 subjects (both PCOS and non-PCOS) will be immediately evaluated to see if any changes are needed in terms of protocol details. The specific points that are to be evaluated are listed below:

1) OGTT with glucose and glycerol tracers

- a. Purpose: Develop an oral stimulus model to assess hepatic and adipose insulin sensitivity.
- i. Question 1. Is 4 hours post oral load long enough to model hepatic and adipose insulin sensitivity?
 1. Rationale: Our preliminary data from OGTT's in obese girls indicates that subjects' insulin and glucose concentrations have not returned to baseline by 2 hours. Data from adults showed that all non-diabetic adults were back to baseline by 3.5 hours.
 2. Measurement. Serum glucose and insulin will be measured post-glucose load for 4 hours in the first 6 subjects. If 4 hours post glucose values are within 10 mg/dL for glucose and 10 IU/mL for insulin relative to baseline values, 4 hours will be considered sufficient.
- ii. We are revising the protocol to 6 hours based on our results from our first several subjects. Question 2: Are glucose and glycerol Ra during the OGTT similar to those obtained with a hyper-insulinemic euglycemic clamp.
 1. Rational: Peak insulin concentrations are similar between an OGTT and a clamp, thus Ra rates should also be similar. Comparisons in adults of the glucose Ra from clamps and an oral meal challenge were similar.
 2. Measurement: The peak suppressed glucose and glycerol Ra for the first 12 subjects will be compared to peak suppressed Ra values calculated from data from 70 girls during hyper-insulinemic euglycemic clamps.
 3. Revision plan if model not correct: None. Findings of either similar or different glucose and glycerol Ra are valuable information.

2) Measurement of Hepatic De Novo Lipogenesis (HDNL)

- a. Purpose: Optimize a model to asses HDNL with minimal blood draws, minimal time of tracer intervention and no interference with measures of glucose and glycerol
 - Ra

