If a subject experiences any of the following, the subject will be withdrawn from the study.

1. Inability to complete study procedures
2. Abnormal screening labs (LFT's >4 times elevate, HbA1C>6.4%, Hg <9 mg/dL)
3. Subject becomes pregnant during study

D. Protocol Stopping Criteria

If one or more subjects experience any of the SAE's listed above, the PI will consult with the mentor prior to continuing study visits with subjects. The mentor and RSA will consult about the significance of the SAE's and make a recommendation to the PI.

VII. Data Analysis Plan:

Statistical Plan for Method Development: The previously described tracer protocol and mathematical modeling with any refinements will be performed in an additional 9 subjects. Outcome measures (raw suppressed glucose and glycerol Ra, insulin concentration required for 50 percent of peak suppression and percent suppression of basal Ra) will be compared between the OG subjects and a matched cohort of girls who have undergone hyperinsulinemic euglycemic clamps with identical glucose and glycerol tracer infusion rates. Subjects in the two groups will be matched on PCOS diagnosis, race, percent body fat, percent liver fat, and time post-menarche. An equivalence design will be used to compare the outcomes in the two groups and to demonstrate whether there are clinically significant differences in outcomes from the OG model and the hyperinsulinemic clamp. For purposes of sample size calculation, we used estimates from the investigator's pilot study. Using an equivalence limit of one standard deviation for each outcome measure (SD=50 units for glycerol IC50 and SD=39 units for glucose IC50) and a correlation of 0.2 between outcomes on matched subjects, 15 matched pairs gives 80% power to demonstrate equivalence. 70 girls have completed the hyperinsulinemic euglycemic clamps, so adequate matching will be possible.

Overall Project Statistical Plan:

Power calculation: The primary outcome is hepatic IR measured as IC₅₀ glucose Ra. Using our preliminary data, a two-tailed t-test and an alpha of 0.05, completing 13 controls and 32 PCOS provides 86% power to detect a difference of 35 IU/L in the insulin concentration.

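### In the oral-versus-clamp equivalence test, raw suppressed Ra and percent suppression are confounded with the insulin level reached, and the premise that peak insulin is similar conflicts with the protocol's own statements.

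*Combined protocol and SAP*

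**What the plan says.** All references are to the combined protocol and SAP.

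- **Premise.** Section IV, item 1, Question 2 compares peak suppressed Ra in the first 12 OG subjects with values from 70 girls who had clamps. Its rationale is that "Peak insulin concentrations are similar between an OGTT and a clamp, thus Ra rates should also be similar".
- **Contrary statements.** Section II.c says that the largest insulin doses that can safely be given intravenously "often produce lower serum insulin concentrations than generated endogenously following an oral glucose load". The preliminary OGTT data in section II.A report that "the PCOS OGTT insulin concentrations are higher than those achieved during the clamp", and the same paragraph names these data as a main reason for moving to an oral model.
- **Equivalence test.** Section VII, Statistical Plan for Method Development, compares OG subjects with matched clamp girls on "raw suppressed glucose and glycerol Ra, insulin concentration required for 50 percent of peak suppression and percent suppression of basal Ra". Taken for glucose and glycerol, that is six measures. Pairs are "matched on PCOS diagnosis, race, percent body fat, percent liver fat, and time post-menarche". The limit is one SD for each outcome, with SDs of 50 (glycerol IC50) and 39 (glucose IC50). With a within-pair correlation of 0.2, 15 pairs are said to give 80% power.
- **Insulin correction.** Section VII, Proposed Isotope Tracer Calculations, says Ra will be shown both with and without a correction for serum insulin. It gives no method and does not mention the equivalence test.

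**The concern.** The protocol relies on unequal insulin to justify the oral test and on equal insulin to explain why the oral test should agree with the clamp. Both cannot hold for the same girls.

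This matters because Ra falls as insulin rises, which is what an IC50 for suppression presupposes. If OG subjects reach higher insulin, their suppressed Ra should be lower and their percent suppression greater than in matched clamp girls, even when the oral method measures Ra without error. The expected difference on those measures is then not zero.

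Two errors become possible. A valid oral method may fall outside the limit because of insulin alone. A method that understates suppression may fall inside it because the extra insulin offsets the bias. In either case the result on those four measures cannot be attributed to the method, which is what Aim 1B wants to know.

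**Working it through.** **1. Which measures are exposed.**

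| Measure (glucose and glycerol) | Referenced to insulin? | Exposure |
|---|---|---|
| Raw suppressed Ra (2) | No | Direct |
| Percent suppression of basal Ra (2) | No | Direct |
| Insulin for 50% of peak suppression (2) | Yes | Smaller; peak suppression may itself depend on the insulin reached |

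The five matching factors do not include insulin reached, and the test has no adjustment for it. Four of the six measures are directly exposed.

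**2. Reproducing the stated power.** Inputs from section VII: n = 15 pairs, limit ±1 SD, correlation 0.2. No alpha is stated for this test; 0.05 per side is assumed, with two one-sided paired t tests.

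- SD of the paired difference = √(2 × (1 − 0.2)) = 1.265 SD.
- Standard error = 1.265/√15 = 0.327 SD.
- t(0.95, 14 df) = 1.761, so the margin of error is 1.761 × 0.327 = 0.575 SD.
- Equivalence is declared when the observed mean difference is within about ±(1 − 0.575) = ±0.425 SD.
- At a true difference of 0, approximate power is 2Φ(0.425/0.327) − 1 = 2Φ(1.30) − 1 = 0.81. The exact calculation, which allows for the estimated SD, gives 0.794.

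The stated 80% is therefore reproduced at zero true difference. With alpha 0.025 per side the exact figure is 62.6%.

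**3. Effect of a shift caused by insulin.** For a true shift θ in SD units, approximate power is Φ((0.425 − θ)/0.327) − Φ((−0.425 − θ)/0.327).

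| Assumed shift θ | Approximate | Exact |
|---|---|---|
| 0 | 0.81 | 0.794 |
| 0.25 SD | 0.68 | 0.68 |
| 0.50 SD | 0.41 | 0.42 |
| 0.75 SD | 0.16 | 0.18 |

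These are probabilities of declaring equivalence on one measure when the oral method itself has no bias.

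**4. Can the actual shift be derived?** No. The shifts above are assumptions. The documents give no SD for suppressed Ra (both SDs are for IC50) and no mean IC50. The two insulin figures do not settle the gap. One is from youth with type 2 diabetes, whose lipolysis persisted "despite very high induced insulin concentrations (200 mU/L"). The other reads "the PCOS OGTT insulin concentrations are higher than those achieved during the clamp 245 ± 40 IU/ml"), where the bracket is incomplete in the available text, so it is unclear which test the figure describes. The OGTT figure is not available.

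**The case against.** **Two analyses should not be merged.** The similar-insulin sentence belongs to the 12-versus-70 comparison in section IV, which names no matching, margin or test and accepts either result as informative. The equivalence test in section VII never invokes that sentence. This stands: deleting the sentence would not change section VII. But the confounding there does not depend on the sentence. It follows from comparing unadjusted Ra when the protocol itself expects higher insulin after the oral load.

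**A reader might infer that the comparison tests insulin and not the method, or that Aim 1B goes unanswered.** The documents do not support that. Raw Ra reflects both. IC50 is also an equivalence outcome, supplies the only SDs in the sample size, and for glucose is the study's primary outcome.

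**The sponsor already foresees an insulin correction.** True, but it is unspecified and not tied to this test.

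**The contrary evidence is limited.** Section II.A concerns girls with PCOS, while the early subjects may or may not have PCOS, and section II.c says only that the gap occurs often. This limits how far the size can be stated. It does not restore the premise, since PCOS is the main study population.

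**Comparing whole protocols is a stated interest.** Aim 1B asks whether oral Ra falls within the clamp range, and section VII looks for differences due to protocol. A descriptive comparison of raw Ra serves that. An equivalence conclusion about the method needs more.

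**Conclusion.** The point holds in limited form. The statements on insulin in sections II and IV contradict each other. In the section VII test, four of six measures confound method with insulin reached; the two IC50 measures are less exposed, though not necessarily free of the problem.

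The stated 80% power reproduces at 79%, conditional on a true difference of zero and an assumed alpha of 0.05 per side. If insulin alone shifted suppressed Ra by 0.25, 0.5 or 0.75 SD, it would be about 68%, 42% or 18%. A reader might take one of these as the expected power; the documents do not support that, because the shift cannot be derived from them. The firm conclusion is qualitative: on the four measures, neither passing nor failing can be credited to the method alone. This should be corrected, but it does not undermine the IC50 comparison.

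**What to change.** 1. Section IV, Question 2: remove the similar-insulin premise and reconcile the rationale with sections II.c and II.A.
2. Section VII, Statistical Plan for Method Development: rest the equivalence conclusion on IC50 and on Ra compared at equal insulin. Do this by specifying the insulin correction already mentioned under the tracer calculations and tying it to this test. One option is to regress Ra on log insulin with a term for method, using the data from the three-stage clamps.
3. Limit that comparison to the insulin range that both tests cover. Where OG insulin exceeds the top clamp stage, reading off a clamp Ra would be extrapolation.
4. Report raw suppressed Ra and percent suppression descriptively.
5. State the alpha, and that the 80% assumes a true difference of zero.

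Cost: analysis wording only, since insulin and Ra are already measured. The price is one assumption about the shape of Ra against insulin, including that changing OGTT insulin can be set beside staged clamp insulin, and the loss of data outside the overlapping range.

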Rationale: We need to assure that the new method produces rates of appearance (Ra) of hepatic glucose release and adipocyte free fatty acid release that are within range of those calculated following the hyperinsulinemic euglycemic clamp which is currently accepted as the gold standard method to assess IR using only an IV approach.

Methods: An additional 9 subjects will be enrolled and studied with the OG model. Data from the raw suppressed glucose and glycerol Ra, insulin concentration required for 50 percent of peak suppression and percent suppression of basal Ra will be compared between OG subjects and a matched cohort of girls whom have already undergone hyperinsulinemic euglycemic clamps with identical glucose and glycerol tracer infusion rates.

Aim 1C: Optimize timing of data collection with ^{31}P -MRS in the liver related to a glucose load.

Rationale: Studies in adults have shown that glycogen synthesis increases by 1 hour post glucose load. A preliminary step to glycogen synthesis or hepatic glucose utilization is passage of glucose

through glucose-6-phosphate (G-6-P). Increased concentrations of G-6-P should be detectable 45 min after a glucose load.

Methods: We will collect ^{31}P data from the liver when subjects are fasted, and 45 min following an 75 gram oral glucose load.

Specific Aim 2: Test the impact of oral glucose on hepatic and adipocyte insulin sensitivity in PCOS, and the effect of common medical therapies metformin and oral contraceptives on hepatic and adipose insulin sensitivity

Rationale: Insulin sensitivity is traditionally assessed with IV only methods. However these do not allow for the contributions of gut hormones, and are non-physiologic. We have previously found significant decreases in hepatic and adipose insulin sensitivity in girls with PCOS and need to determine if this is also seen following a glucose load, as this would be reflective of daily life. Further, the effect of current therapies has not been assessed with this method.

Methods: Perform OGTT's with tracers in obese girls with and without PCOS, and girls with PCOS who have been taking oral contraceptives or metformin.

Specific Aim 3: Determine the role of hepatic and adipose IR in the rate of hepatic de novo lipogenesis (HDNL) and the effect of common medical therapies metformin, oral contraceptives and GLP-1 receptor agonists on HDNL

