The stable isotope method to be utilized is an OGTT with IV glucose and glycerol stable isotope tracers in all subjects, and acetate tracers in select subjects, based on power analysis and cost. For the glucose and glycerol tracers, we will utilize the tracer doses as in our previous hyperinsulinemic clamp studies, as these rates successfully detected basal and stimulated glucose and glycerol Ra. Whole-body lipolysis will be measured under basal conditions and during the OGTT (75 grams glucose + 25 grams fructose + ¹C₁₃ tracer), using a primed (1.6 μ mol/kg), constant (0.11 μ mol/kg/min) infusion of ²H₅glycerol⁴⁷. Hepatic IR will be measured under basal conditions and during the OGTT, using a primed (4.5 mg/kg), constant (0.03 mg/kg/min) infusion of 6,6-²H₂glucose⁴⁸. Blood sampling will continue for 6 hours post-OG to allow return to baseline, based on our pilot data shown in Figure 2 that 2 hours is inadequate. Blood for tracer analysis and glucose and insulin concentrations will be drawn at baseline, every 10 min during the last 40 min of the basal period, and every 15 min post OG load.

The rate of the acetate tracer will be 2 μ mol/kg/min with no prime, based on previous studies⁴⁹. The oral challenge study design is shown in Figure 4. Hepatic De Novo lipogenesis will be measured in the fasting state, and in the fed state following the glucose load, by analyzing the incorporation of the C₁₃ tracer into hepatically secreted lipids such as 16 and 18 carbon long chain

Figure 4: Proposed Oral Glucose Challenge

fatty acids in VLDL⁴⁹. Blood will be drawn at baseline and for the last 4 hours of the basal state and the postprandial state.

A total of 40 girls will receive the overnight acetate infusion. This total will be broken down into 20 un-treated PCOS patients (10 without Byetta and 10 with Byetta), 10 obese control patients and 10 from PCOS patients treated with Metformin or OCP (5 from each group). Analysis of $^2\text{H}_5\text{glycerol}$, 6,6- $^2\text{H}_2$ and long chain fatty acid incorporation of $^2\text{C}_{13}$ Acetate, will be performed by our collaborator [name], using a modification of the negative ion chemical ionization gas chromatography mass spectrometry as in our previous studies^{49,50}.

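### The OG–clamp equivalence test on raw suppressed glucose and glycerol Ra does not adjust for basal Ra, so a basal difference between the non-randomised cohorts can create or hide a method difference

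*Combined protocol and SAP*

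**What the plan says.** Section VII (Statistical Plan for Method Development) names three kinds of outcome for the OG–clamp comparison: "Outcome measures (raw suppressed glucose and glycerol Ra, insulin concentration required for 50 percent of peak suppression and percent suppression of basal Ra) will be" set against those of a matched cohort of girls who have already been clamped. Aim 1B in Section I gives the same list, ending "percent suppression of basal Ra will be compared between OG subjects and a matched cohort".

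On the test and its size, Section VII says:
- "An equivalence design will be used to compare the outcomes in the two groups"
- "Using an equivalence limit of one standard deviation for each outcome measure", where the pilot values are given as "SD=50 units for glycerol IC50 and SD=39 units for glucose IC50"
- for the pairing, "a correlation of 0.2 between outcomes on matched subjects"

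From these it states that 15 matched pairs give 80% power. The matching rule is: "Subjects in the two groups will be matched on PCOS diagnosis, race, percent body fat, percent liver fat, and time post-menarche". Basal Ra is not among the matching factors and no covariate is described. The section does not say which outcome type decides equivalence.

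Basal Ra exists in both cohorts. Section III.C (Visit 3, stable isotope studies) says of the OG girls: "Whole-body lipolysis will be measured under basal conditions and during the OGTT". It sets the same for glucose, with samples every 10 minutes over the last 40 minutes of the basal period. It also reports that the tracer rates carried over from the clamp studies detected basal as well as stimulated Ra.

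**The concern.** The two cohorts are not randomised: one is recruited now and the other has already been studied. Five matching factors, with an assumed pair correlation of only 0.2, leave room for the cohorts to differ in basal Ra. If suppressed Ra tracks basal Ra, any such difference carries into the raw suppressed values and is read as a difference between methods. The offset can act in two directions:

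- If it opposes a real method difference, it can make two unlike methods look equivalent.
- If the methods agree, it can prevent equivalence from being shown.

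Basal Ra is the natural covariate, because it is the same quantity in the same girl, taken before the oral load or the insulin infusion. Percent suppression, listed alongside, divides by basal Ra. It is a separate outcome, however, and does nothing to the test on raw Ra.

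**Working it through.** **Inputs from Section VII:** 15 pairs, margin 1 SD of each outcome, pair correlation 0.2, stated power 80%.

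**Assumed, because the documents do not give them:**
- two one-sided tests at 5% each;
- the same pair correlation of 0.2 for basal Ra;
- rho, the correlation between the pair difference in suppressed Ra and the pair difference in basal Ra;
- a systematic basal offset of 0.5 SD between cohorts;
- a linear relation with one slope.

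**Step 1. Reproduce the plan's figure.** SD of a pair difference = SD × √(2(1 − 0.2)) = 1.265 SD. Standard error of the mean = 1.265/√15 = 0.327 SD. With a true difference of 0 and 14 degrees of freedom, exact power is 79.4%, in agreement with the stated 80%. It is the same for SD 50 and SD 39 because the margin scales with the SD.

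**Step 2. What an offset does to the unadjusted test.** Expected raw difference = method difference + slope × basal offset. In SD units the slope equals rho, so a 0.5 SD offset shifts the raw difference by 0.15, 0.25 or 0.35 SD at rho 0.3, 0.5 or 0.7. If the true method difference is at the margin (1 SD) and the offset opposes it, the expected raw difference is 0.85, 0.75 or 0.65 SD, inside the margin.

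**Step 3. The adjusted test.** Fit (pair difference in suppressed Ra) = a + b × (pair difference in basal Ra) + error. The intercept a is the method difference at equal basal Ra. Residual SD = 1.265 × √(1 − rho²). Variance of a = s² × (1/n + x̄²/Sxx), with n − 2 = 13 degrees of freedom. Here x̄ is the mean of the basal pair differences and Sxx their sum of squares about x̄. The x̄²/Sxx term matters at n = 15: leaving it out overstates the gain from adjustment.

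**Step 4. Results with the 0.5 SD offset** (200,000 simulated studies per setting, margin kept at 1 unadjusted SD):

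| rho | False equivalence, unadjusted | False equivalence, adjusted | Power if methods equal, unadjusted | Power if methods equal, adjusted |
|---|---|---|---|---|
| 0.3 | 11% | 5% | 75% | 71% |
| 0.5 | 18% | 5% | 68% | 81% |
| 0.7 | 27% | 5% | 59% | 94% |

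**Step 5. Power with no offset and methods equal** (unadjusted 79.4% throughout):

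| rho | Adjusted power |
|---|---|
| 0 | 75% |
| 0.2 | 77% |
| 0.3 | 80% |
| 0.4 | 83% |
| 0.5 | 88% |
| 0.6 | 93% |

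Break-even is near rho 0.3. A gain of more than 5 points needs rho slightly above 0.4.

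**Scale of the offset.** The standard error of the mean basal difference is also 0.327 SD, so 0.5 SD is about 1.5 standard errors (0.5/0.327). This gives a sense of scale only. Chance imbalance is already in the standard error of the unadjusted test; the error rates in Step 4 are for a systematic offset.

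**The case against.** Several points can be made on the other side.

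- **The plan does not ignore basal Ra.** Percent suppression indexes each girl to her own basal value, and setting it beside the raw result would expose a basal difference. That stands as a description of the plan. It does not protect the raw-Ra test, and nothing says which outcome prevails if the two disagree.
- **Adjustment is not free.** With 15 pairs it costs power when rho is below about 0.3, and the documents give no rho. This stands. A reader might infer that the planned analysis simply wastes power; that holds only above about 0.3.
- **The 80% figure belongs to other outcomes.** It is illustrated with IC50 SDs, and no SD is given for raw suppressed Ra. This stands. A reader might take the stated power to be wrong; it reproduces.
- **The dinner before the OG study.** A reader might infer that this overfed, high-carbohydrate meal is a known source of a basal difference. The documents do not support that: Section III.C calls the dinner and snack similar to those of the previous studies, and nothing shows that the clamp cohort ate differently.
- **Adjusting changes the question.** Aim 1B asks whether the new method yields Ra values in the range of the clamp. If OG preparation itself moves basal Ra, the intercept removes part of what is being compared. This stands in part, and is a reason to report the unadjusted difference as well.
- **The stakes are modest.** This is method development. Section IV plans no revision whichever way a related comparison of peak suppressed Ra comes out, and the study's primary outcome, glucose IC50, is untouched. This stands.

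**Conclusion.** The point holds for two outcomes, raw suppressed glucose Ra and raw suppressed glycerol Ra, and rests on bias more than on power. The equivalence test compares non-randomised cohorts and leaves out a pre-stimulus measurement available in both. Under the assumed 0.5 SD offset, false equivalence rises from a nominal 5% to between 11% and 27% over rho 0.3 to 0.7. If the methods agree, unadjusted power falls from 79% to between 75% and 59%. Adjustment restores the 5% error rate throughout. It improves power under the offset at rho 0.5 and 0.7, but not at 0.3, where it gives 71% against 75%.

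The offset, rho and the 5% one-sided level are all assumptions, and nothing in the documents shows that a basal offset exists. The conclusion is that the raw-Ra test is open to this error, not that the error will occur. It is a worthwhile refinement and not a fault that undermines the study.

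**What to change.** For raw suppressed glucose Ra and raw suppressed glycerol Ra, prespecify a regression of the within-pair difference (OG minus clamp) on the within-pair difference in basal Ra. Judge equivalence on the 90% confidence interval of the intercept against the existing 1-SD margin. Report the unadjusted raw difference and percent suppression alongside, so that a basal difference between cohorts is visible and not only adjusted away. State which outcome type decides equivalence. Leave the IC50 comparison as planned.

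The cost is one covariate, one degree of freedom and a change of wording in Section VII, with no new data or subjects. With no basal offset, the power cost is about 2 to 3 points if rho is 0.2 and about 5 points if rho is 0.
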